## 1. Background and Rationale

Chronic subdural hematoma (cSDH) is a common condition, particularly in older adults. The standard treatment typically consists of surgical decompression (burr-hole craniotomy). However, recurrence rates following surgery alone reach up to 30%.

Middle meningeal artery embolization (MMAE) is a minimally invasive therapy that can significantly reduce the risk of recurrence. Initial randomized controlled trials and meta-analyses demonstrate high efficacy and safety. Nevertheless, prospective, standardized data on patient selection, prognosis, and follow-up remain lacking.

The PRO-EMMA study aims to establish and evaluate a prospective, standardized follow-up protocol.

## 2. Objectives

**Primary:** To identify clinical and radiological predictors of good functional outcome (mRS  $\leq 2$  at 90 days) after MMAE for cSDH.

**Secondary:**

- Reduction of hematoma volume over time (follow-up CTs)
- Assessment of complications, re-interventions, and mortality
- Validation of a standardized follow-up protocol (CT + clinical/QoL assessments)

**Primary Endpoints:**

1. **Radiological response** – Change in hematoma volume/thickness at 3 months
2. **Clinical efficacy** – Re-intervention rate and functional outcome (mRS) at 90 days
3. **Clinical safety** – Occurrence of complications

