**Potential Confounders (Core Set):**

- Hematoma architecture
- Initial volume/thickness and localization
- Foramen spinosum diameter
- Anticoagulation / antiplatelet therapy
- Extent of embolization (vessel-branch level; embolic agent documented)

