## 3. Study Design

Prospective, single-arm, single-center registry.

Duration: 12 months recruitment.

Target population: 75–150 patients.

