## 4. Eligibility Criteria

**Inclusion Criteria:**

- CT- or MRI-confirmed chronic subdural hematoma (cSDH)
- Planned or completed MMAE (primary therapy or adjunct to surgical evacuation)
- Age  $\geq 18$  years
- Written informed consent including agreement to extended follow-up (CT and clinical assessments)

- mRS  $\leq 3$  at baseline

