## **6. Data Collection**

**Clinical:** Medical history, GCS, comorbidities, anticoagulation/antiplatelet therapy, symptom course

**Radiological:** Hematoma volume, architecture, laterality, localization, midline shift, MMA caliber, anatomical MMA variants, foramen spinosum diameter, prior burr-hole trepanation

**Procedural:** Embolic agent, BE-EMMA score, technical details, embolisation volume, degree of distal penetration, complications

**Follow-up:** mRS, GOS-E, EQ-5D-5L, GCS, Markwalder score at each time point; re-intervention, recurrence, mortality, symptom course

Documentation is performed in pseudonymized case report forms (CRF; currently Excel-based, with planned migration to REDCap).

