## 10. Statistics

Target sample size: 75–150 patients (exploratory).

Descriptive statistics with 95% confidence intervals; bivariate correlation analyses (Pearson or Spearman); logistic regression for predictor analysis. Missing data will be reported but not imputed.

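### Surgical evacuation is missing from the confounder core set, and the volume-change endpoint fixes neither its reference scan nor how a CT after re-operation counts

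*Protocol*

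**What the plan says.** Protocol section 3 describes the study as "Prospective, single-arm, single-center registry". Section 4 admits two treatment settings into it: "Planned or completed MMAE (primary therapy or adjunct to surgical evacuation".

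Section 2 gives the radiological primary endpoint as "Change in hematoma volume/thickness at 3 months" and the clinical efficacy endpoint as "Re-intervention rate and functional outcome (mRS) at 90 days". It then states a core set of five potential confounders: hematoma architecture, starting size and site, foramen spinosum width, blood-thinning drugs, and "Extent of embolization (vessel-branch level; embolic agent documented". Surgical evacuation is not among them.

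Surgery does appear in section 6, where the radiological items end with "foramen spinosum diameter, prior burr-hole trepanation", and re-intervention is a follow-up item. Neither is assigned to an analysis. Section 10 names descriptive statistics, "bivariate correlation analyses (Pearson or Spearman"), logistic regression for predictors, and no imputation.

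Section 5 times the clinical baseline before the intervention and schedules CTs only after it (within 7 days, and at 3 months). Section 4 excludes patients without baseline radiological data, but no section places the baseline CT before or after evacuation.

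**The concern.** Evacuation physically removes the quantity that the radiological endpoint measures. It differs between the two enrolled settings by definition, and it is a plausible confounder of mRS at 90 days, the outcome in the primary objective. A protocol that writes down its confounders, and includes foramen width but not surgery, has fixed the list badly. An analysis that follows the list cannot separate predictors of outcome after MMAE from markers of having been operated on.

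Two further gaps bear on the volume result itself.

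- If the reference scan precedes an index evacuation, drained blood is counted as response to MMAE.
- If a patient is re-operated between MMAE and the 3-month CT, that CT shows the result of the second operation. The patient is a failure on re-intervention and may look like a marked improvement on volume.

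At stake is the headline volume reduction in a study with no comparator to expose the problem. An unnamed reference scan also leaves room to choose between scans once the data are seen.

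**Working it through.** **No plan figure to reproduce.** The target of 75–150 patients (section 10) is labelled exploratory and carries no variance, effect size or event rate. The check is therefore textual, followed by an illustration on assumed inputs.

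**Text**

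- Sections 3 and 4 together put both settings in one cohort with no stated strata.
- The core set in section 2 has five items and none is surgery. The surgical item in section 6, "prior burr-hole trepanation", covers earlier surgery and may not capture evacuation done after MMAE.
- A surgical re-intervention after MMAE necessarily falls after any pre-MMAE reference scan. If it occurs before the 3-month CT, it lies inside the measured interval. This holds whichever pre-MMAE scan is chosen.
- Section 5 makes no exception for re-operated patients. The no-imputation rule in section 10 does not remove their CT, because a CT taken after re-operation is not missing.

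**Illustration A: adjunct surgery with a pre-operative reference**

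Assumed: reduction after MMAE alone m = 30–50%; fraction evacuated e = 50–70%; adjunct share s = 20–80%.

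Pooled mean = (1 − s)m + s[1 − (1 − e)(1 − m)], so the excess over m is s × e × (1 − m).

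| s | e | m | Excess | Pooled mean |
|---|---|---|---|---|
| 0.2 | 0.5 | 0.5 | 0.2 × 0.5 × 0.5 = 0.05 | 55% |
| 0.5 | 0.5 | 0.5 | 0.5 × 0.5 × 0.5 = 0.125 | 62.5% |
| 0.8 | 0.7 | 0.3 | 0.8 × 0.7 × 0.7 = 0.392 | 69.2% |

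The range is 5 to 39 percentage points. With a post-operative reference the excess in this model is 0.

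**Illustration B: re-operation before the 3-month CT**

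Assumed: re-operation rate q = 5–10%; growth before re-operation g = 0–20%; fraction then evacuated e = 60–80%; m = 50% in everyone else; every re-intervention is surgical.

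Apparent reduction in a re-operated patient = 1 − (1 + g)(1 − e). This runs from 1 − 1.2 × 0.4 = 52% to 1 − 1.0 × 0.2 = 80%. On the scan before re-operation the same patient shows −g, that is 0 to −20%.

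Difference in the pooled mean between the two choices = q × e × (1 + g):

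- q = 5%: 0.05 × 0.6 × 1.0 = 0.030 to 0.05 × 0.8 × 1.2 = 0.048
- q = 10%: 0.10 × 0.6 × 1.0 = 0.060 to 0.10 × 0.8 × 1.2 = 0.096

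The range is about 3 to 10 points. The only related rate in the protocol is recurrence of up to 30% after surgery alone (section 1), which is not a rate after MMAE. As an outer bound, q = 30% gives 0.18 to 0.288.

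**Scale.** The 95% half-width for a proportion of 50% is 1.96 × √(0.25/75) = 11.3 points at 75 patients and 1.96 × √(0.25/150) = 8.0 points at 150. This is a yardstick only: the endpoint is a change in volume, whose SD the protocol does not give.

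**The case against.** The strongest reply is that much of this is silence. Section 10 is a short list of methods with no covariates for any model. Strata, model terms, the reference scan and the handling of later events are commonly left to a SAP, which may exist. The registry is labelled exploratory, surgery and re-intervention are recorded, and re-interventions stay visible in their own primary endpoint. Reporting 3-month volume whatever happened in between is a legitimate treatment-policy choice. If the reference is the last CT before MMAE, earlier surgery contributes nothing.

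Most of that stands, and it rules out several stronger readings that a reader might infer:

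- *The settings are pooled and re-operated patients keep their 3-month CT.* The protocol states neither.
- *Treatment failures count as responders.* There is no responder category; the endpoint is a change with no threshold.
- *The endpoint measures mainly surgery.* In Illustration A the surgical part is 5 of 55 points (9%) at the low end and 39.2 of 69.2 (57%) at the high end. More than half needs the extreme assumed inputs together with a pre-operative reference.
- *The plan correlates change with initial volume, which are mathematically coupled.* No section plans that correlation; the stated predictor objective concerns mRS, and initial volume is in the core set.

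The reply does not reach the core set. That list is stated, not left open, and it omits evacuation. Nor does it remove the overlap between re-operation and the 3-month CT.

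**Conclusion.** The point holds in bounded form. The protocol enrols two settings that differ in surgical evacuation and fixes a confounder list without it. The change endpoint also has no named reference scan and no stated place for a CT taken after re-operation.

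The omission from the core set rests on the text alone. The sizes do not. The 5–39 points require a pre-operative reference and the assumed adjunct share, evacuated fraction and MMAE effect. The 3–10 points require a 5–10% surgical re-operation rate and retention of the later CT. Across parts of these ranges the shift is as large as the rough precision yardstick for 75–150 patients, and recruiting more patients would not shrink it. No figure in the protocol is contradicted. It is a specific correction, best settled before data accrue, and not proof that the results will be biased.

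**What to change.** 1. Add standalone versus adjunct MMAE to the core set in section 2 and use it in the predictor models. Report volume change and the other primary endpoints separately by this indicator. Record when evacuation took place relative to MMAE.
2. Name the reference CT as one taken after any index evacuation: the last available CT before MMAE when surgery came first, and the first post-evacuation CT otherwise. The scan within 7 days cannot be assumed to serve, because it is timed from MMAE and may precede a later evacuation.
3. Report 3-month volume change with patients re-intervened before that CT shown separately, or analysed with their last available CT before re-intervention. Give this alongside the analysis that keeps the 3-month CT.
4. If predictors of volume are analysed, regress 3-month volume on reference volume and the surgery indicator.

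Cost: mainly wording, plus one CRF field. The strata will be smaller and the headline reduction probably less favourable. Two limits should be stated. The last CT before re-intervention is not a scheduled scan and may be unavailable. Where evacuation follows MMAE, a post-evacuation reference drops any change between the two procedures. Clinical care is unaffected.

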**Secondary Endpoints:**

- Symptom course over time
- Need for re-hospitalization
- Mortality

**Potential Confounders (Core Set):**

- Hematoma architecture
- Initial volume/thickness and localization
- Foramen spinosum diameter
- Anticoagulation / antiplatelet therapy
- Extent of embolization (vessel-branch level; embolic agent documented)

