#### **Study-specific additional assessments:**

##### **Clinical and quality-of-life assessments** (mRS, GOS-E, EQ-5D-5L, GCS, Markwalder score):

- Pre-interventionally (baseline)
- Day 30 (telephone interview)
- Day 90 (in-person or telephone, within the new cSDH outpatient clinic)
- Day 120 (telephone interview)

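### Baseline mRS is missing from the core confounder set, although patients entering at mRS 0–2 already meet the Day-90 good-outcome definition

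*Protocol*

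**What the plan says.** The primary objective in Section 2 is "To identify clinical and radiological predictors of good functional outcome", defined as mRS ≤2 at 90 days. This is an absolute threshold, not a change from the starting value.

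Section 4 admits patients with "mRS $\leq 3$ at baseline" and sets no lower limit, so mRS 0, 1, 2 and 3 are all eligible.

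Section 2 then gives a list headed "Potential Confounders (Core Set". Its five entries cover haematoma architecture; initial size and location; foramen spinosum diameter; "Anticoagulation / antiplatelet therapy"; and extent of embolization. The antithrombotic entry is the only one about the patient's clinical state. No functional or neurological score is listed.

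Section 5 schedules mRS, together with GOS-E, EQ-5D-5L, GCS and the Markwalder score, at a time point labelled "Pre-interventionally (baseline".

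Section 10 names bivariate correlations and "logistic regression for predictor analysis" without covariates, and gives "Target sample size: 75–150 patients (exploratory") as the size. Section 3 describes a "Prospective, single-arm, single-center registry".

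**The concern.** The baseline value of an outcome scale is usually among the strongest determinants of its later value. Here the link is built into the definitions: three of the four eligible baseline levels already satisfy the outcome. For patients at mRS 0–2 a good outcome means not getting worse; for patients at mRS 3 it means improving. The analysis pools the two.

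If baseline mRS is left out of the models, any factor that goes with worse starting function (larger volume, certain architectures, antithrombotic use) can be associated with Day-90 mRS through that route alone. There is no comparator arm in which starting function would be balanced. Section 9 says the results should improve patient selection and treatment planning. For that use, a reader needs to know whether a factor tells more than the patient's mRS at entry already does.

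**Working it through.** **Reading check.** The eligible levels are mRS 0, 1, 2, 3, and the outcome is mRS ≤2, so levels 0–2 meet it at entry. Baseline mRS is in the Section 5 schedule but not in the Section 2 core set. Sections 2 and 10 contain no adjustment for baseline mRS, no stratification by it, and no shift or change definition of the outcome.

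**Inputs.** The protocol gives no baseline mRS distribution, outcome rate or factor prevalence, so there is no stated figure to reproduce. Everything below is an assumption used for illustration:
- f = share entering at mRS ≤2
- a = probability of a good outcome if baseline mRS ≤2
- b = probability of a good outcome if baseline mRS 3

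**Odds ratio of baseline mRS (≤2 versus 3) for good outcome** = [a/(1−a)] / [b/(1−b)].
- a = 0.90, b = 0.60: 9/1.5 = 6.0
- a = 0.90, b = 0.50: 9/1 = 9.0
- a = 0.95, b = 0.40: 19/0.667 = 28.5
- a = 0.75, b = 0.70: 3/2.333 = 1.3

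Over a = 90–95% and b = 40–60% the range is 6–28.5. With weak dependence it is close to 1.

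**Share of good outcomes that were already good at entry** = fa / [fa + (1−f)b].
- f = 0.4, a = 0.90, b = 0.60: 0.36/0.72 = 50%
- f = 0.6, a = 0.90, b = 0.50: 0.54/0.74 = 73%
- f = 0.8, a = 0.95, b = 0.40: 0.76/0.84 = 90%
- f = 0.3, a = 0.75, b = 0.70: 0.225/0.715 = 31%

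**Crude odds ratio of a factor with no effect.** Take f = 0.6, a = 0.90, b = 0.50, with the factor present in 30% of mRS ≤2 and 60% of mRS 3 patients. Per 100 patients:

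| | Factor present: poor / good | Factor absent: poor / good |
|---|---|---|
| Baseline mRS ≤2 (60) | 1.8 / 16.2 | 4.2 / 37.8 |
| Baseline mRS 3 (40) | 12 / 12 | 8 / 8 |
| Pooled | 13.8 / 28.2 | 12.2 / 45.8 |

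The odds ratio is 1.0 in each row. Pooled, it is (13.8 × 45.8)/(28.2 × 12.2) = 632.04/344.04 = 1.84 for poor outcome.

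With the same f and prevalences but a = 0.75 and b = 0.70, the pooled counts are 11.7/30.3 and 15.3/42.7. The odds ratio is 499.59/463.59 = 1.08.

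**Sensitivity with a larger imbalance** (f = 0.5; factor present in 30% versus 70%), crude odds ratio for poor outcome:

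| a / b | Factor present: poor / good | Factor absent: poor / good | Crude odds ratio |
|---|---|---|---|
| 0.75 / 0.70 | 14.25 / 35.75 | 13.25 / 36.75 | 1.11 |
| 0.90 / 0.70 | 12 / 38 | 8 / 42 | 1.66 |
| 0.90 / 0.50 | 19 / 31 | 11 / 39 | 2.17 |
| 0.95 / 0.40 | 21.75 / 28.25 | 10.75 / 39.25 | 2.81 |

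Adjusting for the two baseline groups returns 1.0 in every row, by construction.

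**Poor outcomes available** (f = 0.6, a = 0.90, b = 0.50).
- N = 75: 45 × 0.10 = 4.5 in the mRS ≤2 group and 30 × 0.50 = 15 in the mRS 3 group, 19.5 in all.
- N = 150: 9 and 30, 39 in all.

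**The case against.** **The list is not declared to be the regression covariates.** Section 2 speaks of potential confounders. It does not say that the list is exhaustive or that other variables are barred. Baseline mRS could enter as one of the clinical predictors named in the objective, and a statistical analysis plan, not shown here, may add it. This stands as far as it goes: one may not infer that the analysis is bound to omit baseline mRS. But the protocol does fix a core set, and the set lacks the baseline value of the outcome scale itself. An analysis plan that follows it would inherit the gap. Testing baseline mRS as one candidate among many is also not the same as adjusting the other factors for it.

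**Prediction is not causation.** In an exploratory single-arm registry, a factor that marks worse starting status can still predict outcome validly. This also stands. What is lost is evidence of value beyond baseline function, not the truth of the prediction. The protocol's own use of the word confounders nevertheless shows that adjusted associations are intended.

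**The size is assumed.** A reader might infer that the analysis will mostly rediscover who was already well. The protocol does not support that, because it gives neither the baseline distribution nor the outcome rates. With weak dependence the distortion is small.

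**Stratified models would not be feasible.** With about 4.5–9 poor outcomes in the mRS ≤2 group, predictor models within that group cannot be fitted sensibly. This stands and limits the fix to description by group.

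**Conclusion.** The omission is confirmed from the text: entry criterion and outcome threshold overlap, baseline mRS is collected, and it is absent from the named core set with nothing else in the protocol to make up for it. The consequence is a risk, not a certainty. Factors that mark starting disability may appear as predictors of outcome after embolization, and what they add to baseline function would not be shown.

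Its size rests wholly on assumed rates: a crude odds ratio of 1.84 for a factor without effect in the central scenario, about 1.1 under weak dependence, and up to 2.8 in the strongest case examined. The exploratory label excuses limited precision, but not a bias that a variable already collected can reduce. No stated figure is wrong and no data would be lost, so this is a point that should be fixed rather than one that must be.

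**What to change.** 1. Add baseline mRS to the core confounder list in Section 2.
2. State in Section 10 that every logistic model of Day-90 mRS ≤2 includes baseline mRS as a single score term (0–3). This assumes an approximately linear effect on the log odds, which should be said.
3. Report the Day-90 outcome descriptively, with confidence intervals, separately for baseline mRS ≤2 and baseline mRS 3. Do not fit predictor models within these groups.

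The cost is a few lines of wording and one model degree of freedom, set against about 20–40 poor outcomes in the central scenario. That is a real charge on a small model that already has five multi-part core items, so other terms may have to be limited. No new data are needed: baseline mRS is in the Section 5 schedule, and Section 4 already excludes patients with incomplete baseline data. Adding age, and a supportive ordinal model of the full Day-90 mRS, are reasonable options but not required to settle this point.

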## 3. Study Design

Prospective, single-arm, single-center registry.

Duration: 12 months recruitment.

Target population: 75–150 patients.

## 4. Eligibility Criteria

**Inclusion Criteria:**

- CT- or MRI-confirmed chronic subdural hematoma (cSDH)
- Planned or completed MMAE (primary therapy or adjunct to surgical evacuation)
- Age  $\geq 18$  years
- Written informed consent including agreement to extended follow-up (CT and clinical assessments)

- mRS  $\leq 3$  at baseline

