#### **Exclusion Criteria:**

- Acute subdural hematoma requiring emergency neurosurgical intervention
- Known vascular anomalies contraindicating embolization (e.g., high-risk leptomeningeal anastomoses)
- Missing or incomplete baseline clinical and radiological data
- Unavailability for prospective follow-up (e.g., no fixed address, no telephone contact)

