##### **Imaging follow-up** (cranial CT):

- Within 7 days post-intervention
- At 3 months post-intervention (within the new cSDH outpatient clinic)

**Note:** Compared to the currently heterogeneous clinical routine at the Charité, these assessments may result in one additional CT for some patients. The chosen time points are fully consistent with the recommendations of the international ARISE-I consensus, which endorses early follow-up imaging and a 3-month control CT. The use of ionizing radiation in this study has been approved in accordance with the German Radiation Protection Act (Strahlenschutzgesetz) and the applicable regulatory requirements of the Federal Office for Radiation Protection (Bundesamt für Strahlenschutz, BfS).

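### Enrolment after a completed MMAE, with no time limit, can leave early deaths and incapacitating complications out of the safety and outcome rates

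*Protocol*

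**What the plan says.** Section 3 of the protocol describes a "Prospective, single-arm, single-center registry". Section 4 admits patients with "Planned or completed MMAE (primary therapy or adjunct to surgical evacuation", so enrolment may come before or after the procedure. It also requires "Written informed consent including agreement to extended follow-up (CT and clinical assessments" and a baseline mRS of at most 3. The exclusion criteria remove patients with "Missing or incomplete baseline clinical and radiological data" and those with "Unavailability for prospective follow-up (e.g., no fixed address, no telephone contact".

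Section 5 times the first mRS, GOS-E, EQ-5D-5L, GCS and Markwalder assessments as "Pre-interventionally (baseline" and lists them among the study-specific additions. The first follow-up CT is due "Within 7 days post-intervention", and the first telephone interview is on day 30.

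In Section 2, "Occurrence of complications" is the primary safety endpoint, re-intervention and day-90 mRS make up the primary efficacy endpoint, and mortality is secondary. The primary objective is to find predictors of mRS 2 or less at day 90.

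The protocol states no maximum interval from MMAE to enrolment, no proxy or deferred consent, no consecutive enrolment and no log of procedures. It does not distinguish patients enrolled before MMAE from those enrolled after it.

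**The concern.** The clock for complications, mortality and day-90 outcome starts at the procedure, but a patient with a completed MMAE enters only at consent. To reach consent the patient must be alive and able to give it. The interval between the two is immortal time for the late enrollee, and the events most likely to fall in it (early death, incapacitating complication) are the ones a safety description most needs.

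This cannot be repaired at the analysis stage. Section 10 promises to report missing data, but a patient who was never enrolled or logged is not a missing value. The loss does not shrink with a larger sample, and the planned 95% confidence intervals do not reflect it.

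There is also an internal conflict. A study-specific assessment due before the intervention cannot be made prospectively in someone first approached afterwards.

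**Working it through.** **Setting the sections side by side.**

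1. Entry is allowed after MMAE (Section 4), without a window. Written consent is required and no substitute for the patient's own consent is described. Death or loss of capacity before consent therefore bars entry.
2. A surviving, capable patient who has had a recurrence, a re-intervention or a non-disabling complication can still sign. The barrier does not apply to them.
3. Baseline is pre-interventional (Section 5). For a late enrollee, GCS, imaging and perhaps mRS may be taken from routine records made before the procedure. EQ-5D-5L is self-reported, so it is either recalled with the early course known or absent.
4. With no window, a late enrollee may also have passed the 7-day CT or the day-30 interview.

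**Illustration of size.** The protocol has no figure to reproduce: the target of 75–150 is called exploratory and no event rate is given. All three inputs below are assumptions.

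- p = true risk of early death or incapacitating complication
- c = share of treated patients approached only after MMAE
- q = share of event patients in that group lost before consent

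The share of all treated patients lost is L = p × c × q. The observed risk is (p − L) / (1 − L).

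With p = 5% and c = 0.5:

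| q | L | Observed risk |
|---|---|---|
| 0.5 | 0.0125 | 0.0375 / 0.9875 = 3.8% |
| 0.8 | 0.0200 | 0.0300 / 0.9800 = 3.1% |
| 1.0 | 0.0250 | 0.0250 / 0.9750 = 2.6% |

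The last row is the upper bound of the bias for this p and c. With c = 0.25 and q = 0.5, L = 0.00625 and the observed risk is 0.04375 / 0.99375 = 4.4%.

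For p from 2% to 10%, c from 0.25 to 1 and q from 0.25 to 0.8, the observed risk is about 0.20 to 0.94 times the true risk. Under this model it is always too low. It equals the true risk if c = 0 (everyone consents before MMAE) or q = 0 (nobody is lost).

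**Day-90 good outcome.** If none of the lost patients would have reached mRS 2 or less, the observed proportion is the true one divided by 1 − L. For the three table rows this is a factor of 1/0.9875 = 1.013, 1/0.98 = 1.020 and 1/0.975 = 1.026. At a 5% early risk, the relative effect on good outcome is far smaller than the effect on the early event risk.

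**Against sampling error.** Exact 95% intervals are 1.5% to 13.1% for 4 events in 75 and 2.3% to 10.2% for 8 in 150. In this illustration the bias is smaller than the random uncertainty, but it runs in one direction and the interval gives no sign of it.

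**The case against.** The strongest reply is that the late-enrolled share may be small. The criterion may have been meant for patients approached within a day or two of the procedure. If the exclusion for incomplete baseline data is applied strictly to all the Section 5 instruments, few late patients would qualify at all. The study is exploratory and descriptive, with no confirmatory test to be invalidated. This stands as a limit on size. It does not close the route, because no window is written down, and strict exclusion would contradict the criterion that admits completed cases.

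A reader might also infer more than the protocol supports:

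- *That all patients with early failure or re-intervention are lost.* They are not: a capable survivor can consent. Neither loss nor its direction is shown for re-intervention.
- *That about half the early risk disappears.* This needs half the patients to be approached late and every one of their events to be lost. The protocol supports neither.
- *That every late enrollee lacks a baseline and must be excluded.* The exclusion speaks of clinical and radiological data, while Section 5 names quality of life alongside clinical assessments, so a missing EQ-5D-5L need not trigger it. Most other items may be in the chart. EQ-5D-5L is also not among the listed endpoints.
- *That patients worsened by a complication fail the mRS criterion.* This would follow only if mRS were scored at enrolment, and Section 5 places baseline before the intervention.
- *That the predictor model is shown to be biased.* Selecting early survivors can distort associations. Whether it does depends on how the predictors relate to early events and to late enrolment, which the protocol does not show.

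**Conclusion.** The concern holds in a limited form. As written, the protocol lets early deaths and incapacitating complications go uncounted among patients enrolled after MMAE. Mortality and the disabling part of the primary safety endpoint can be understated, and day-90 good outcome overstated. The direction follows from the consent requirement. The size cannot be derived, because neither the late-enrolled share nor the early event risk is given. The figures of 3.8%, 3.1% and 2.6% against a true 5% are illustrations that assume half the patients are approached late; the last is the extreme case in which all of their events are lost.

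The baseline conflict is real for EQ-5D-5L. For the other instruments it depends on what routine records hold. The prospective label does not fully describe patients entered after the procedure.

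**What to change.** Preferred: restrict inclusion to planned MMAE, with consent and the Section 5 baseline obtained before the procedure, and count events from the day of the procedure.

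If completed cases are to be kept:

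- state a maximum interval from MMAE to enrolment;
- record for each patient whether enrolment came before or after MMAE;
- base the complication, mortality and good-outcome rates on patients enrolled before MMAE, and report completed cases separately;
- fit the predictor model with and without completed cases.

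In either case, report the number enrolled against the count of all MMAE procedures for chronic subdural hematoma at the centre during the recruitment period.

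The cost is a short amendment to Section 4 and a procedure count at one centre. The main analysis will have fewer patients, by an amount the protocol does not allow to be estimated: it gives no accrual figure and no late-enrolled share, so it cannot be assumed that the 75–150 target absorbs the loss. The change is best made before recruitment starts, since early events that were not logged may not be recoverable later.
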